***Exclusions based upon in-person screening:***

1) Mild or worse dementia defined by a Clinical Dementia Rating (CDR) score  $\geq 1^{122}$  as reviewed by a board certified neuropsychologist ([name]), or 2) gait disorders due to Parkinson's disease, foot drop, lower-extremity deformity, joint replacement or severe arthritis, as identified during a gait evaluation conducted by a research nurse ([name]) and reviewed by a geriatrician and falls specialist ([name]).

## Participant recruitment

---

### *Describe recruitment methods*

We have full confidence that we can identify and recruit 144 individuals that meet the study criteria.

We will utilize a multi-pronged approach to meet our recruitment goals.

1. We will advertise the study in the community via newspaper and posted advertisements.
2. We will post the study on websites, e.g., including the Institute for Aging website; clinicaltrials.gov; and craigslist.
3. We will send a standardized letter to potentially eligible participants from the Mobility and

4.5

Brain Function Database. We will avoid over-burdening individuals within the repository by only contacting those individual who have not participated in other studies within the past 6 months.

4. We will advertise within the Hebrew SeniorLife housing sites by hanging flyers within common areas, and advertising in community newsletters.
5. We will conduct community presentations at senior housing sites.
6. We will utilize the Harvard Catalyst (CTSA) Shared Health Research Information Network (SHRINE) to identify volunteers with recent falls from Harvard-affiliated hospitals and clinics.

#### **Attach all recruitment materials**

---

[Recruitment\\_Flier\\_v1 071218.pptx](#)

#### **Procedures for obtaining informed consent**

---

*Include who will obtain consent and the timing of consent from recruitment*

4.6 Interested individuals will be asked to provide verbal consent to complete initial eligibility screen during a phone conversation with study personnel. Potentially eligible participants will then schedule an in-person screening procedure. Potential participants may be emailed or snail-mailed (per request, and according to their preference) a copy of the informed consent for them to review at their own pace prior to the in-person screening. Written informed consent will be obtained by study personnel at the beginning of this in-person screening procedure.

#### **Are you requesting a waiver of any required element of informed consent?**

---

**Yes:** *Complete Form B - Consent Waiver Request*

No

#### **Attach the informed consent form(s)**

---

*Please download the sample consent form, fill it out and then upload attachment here.*

[Personalized tDCS in Fallers.v3\\_81518\\_ICF IRB edits track changes.docx](#) Sample  
[Personalized tDCS in Fallers.v3\\_8152018\\_ICF clean.docx](#) documents:  
[Sample\\_ICF REV 3.29.16.docx](#)

#### **Withdrawal of participants**

---

*Include any anticipated circumstances when participants will be withdrawn without their consent, how participants will be withdrawn, including use of any collected data and follow-up with any new/pertinent information.*

4.7

If during the course of their study enrollment, a participant develops a new medical condition that would make participation in the study contraindicated, as determined by a study physician ([name]), the participant will be informed of this and withdrawn from the study. All data collected prior to withdrawal will be maintained in the study data set.

**4.8 Will you be enrolling participants who may have diminished capacity to provide informed consent or to understand study procedures (now or in the foreseeable future)?**

---

Yes

No

**4.9 Will non-English speakers be enrolled in the study?**

---

Yes

No

**5.0 Study Procedures**

---

**List the number of study visits, including procedures/tests involved at each visit**

---

*e.g. blood test, x-rays, questionnaires. If numerous study visits and procedures are involved, include a study procedure timeline.*

Participants will be asked to complete 26 visits over 8 months. All study visits, except the MRI visit, will take place at the Clinical Research Laboratory at Hebrew Rehabilitation Center, Roslindale MA. The MRI visit, visit 2, will take place at the Beth Israel Deaconess Medical Center, in the MRI Suite, [name]. Free parking or transportation will be provided for all study visits.

**Visit 1—In-person screen and study familiarization (Up to 2.5 hours) at the Clinical Research Laboratory at Hebrew Rehabilitation Center, Roslindale, MA.** Individuals deemed potentially eligible via phone screen will complete an in-person screen. All screening assessments, other than the physical exam and the CDR scale, will be administered by trained research assistants. Individuals will read and sign an informed consent form approved by the Hebrew SeniorLife IRB. A medical history questionnaire will be complete and medications, blood pressure, height, body mass and years of education will be recorded. The SPPB and the TMT will be completed to ensure at least mild performance decrements in physical and executive

function. [name] or a trained clinician will then administer the CDR to characterize cognitive status and rule out dementia. [name] or a trained clinician will conduct a physical, neurological exam, and clinical gait assessment to rule out acute illness and overt neural or musculoskeletal causes of falls. Individuals who meet all inclusion and exclusion criteria will be enrolled. Participants will then complete the Physical Activity Scale for the Elderly to obtain self-reported levels of baseline physical activity, and the WTAR single word reading test of premorbid intellectual ability (1-minute administration time, to be used as an adjustor for changes in executive function).

**Familiarization:** At the end of Visit 1, participants will first complete the proposed cognitive assessment battery **as practice** to *minimize the effects of procedural learning following the true baseline* to be completed during Visit 3 (see that section for battery details). Trained research assistants will administer the familiarization testing. They will not repeat the TMT, nor will they practice the Montreal Cognitive Assessment (MoCA) because it has multiple test versions that minimize confounding due to learning. Second, they will complete a 20-30 minute familiarization of the dual task paradigm (see “Dual task performance” subsection below). This procedure will 1) determine the cognitive task to be used in the assessment, thereby ensuring that it is not too difficult and/or anxiety provoking to the participant, and 2) minimize the potential for procedural-related learning to influence outcomes. First, we will determine the cognitive task to be used for each participant using a standardized procedure in which participants are seated in a chair and asked to count backwards from 200, first by 7’s, then 3’s, 5’s, or 1’s. The first task in which three correct answers are provided within 15 sec will be used for testing. Participants will also receive instructions on the specific dual task testing procedures and complete several practice trials of each condition.

**Visit 2—Structural MRI (Up to 1 hours):** Baseline MRIs will enable personalization of tDCS via current flow modeling, as well as detection of silent infarcts and white matter hyperintensities (WMHs). T1, T2, and T2-weighted fluid-attenuated inversion recovery (T2 FLAIR) scans will be completed on a 3T GE system with a quadrature head coil at the Beth Israel Deaconess Medical Center, located near the Clinical Research Lab. The MRI scan itself will last 30 minutes.

**Visit 3—Baseline assessments (Up to 2.5hrs)** at the Clinical Research Laboratory at Hebrew Rehabilitation Center, Roslindale, MA :

This assessment will take place within IFAR’s Clinical Research Laboratory and comprise tests of dual tasking, mobility, and cognition. Trained research assistants will administer all of the baseline assessment testing described below. Accelerometry-derived habitual physical activity will be assessed for five days after baseline. Falls-tracking will also be initiated at this visit.

**Dual task performance:** Procedures will follow published recommendations that produce excellent test-retest reliability. We have used this paradigm within our research and laboratory for over ten years. Participants will complete three, 60-second trials in each of five conditions:

- Condition 1: Single task: seated cognitive task (see below for description).
- Condition 2: Single task: standing.
- Condition 3: Single task: walking.

- Condition 4: Dual task: standing with cognitive task.
- Condition 5: Dual task: walking with cognitive task.

All standing trials will be completed on a stationary force plate (Kistler, Inc) to record postural sway (i.e., center of pressure) fluctuations throughout the trial. Participants will stand barefoot with arms at their side and feet shoulder width apart. The feet will be traced on the first trial and this tracing will be used to ensure consistent foot place throughout the study. Participants will be instructed to focus their attention on an “X” marked on a wall in front of them at eye level and will be reminded to stand as still as possible before each trial. All walking trials will be completed around a 25m indoor track. Prior to testing, participants will be outfitted with wireless biosensors—each containing a triaxial accelerometer, goniometer and magnetometer—on the sternum, low back, wrists and ankles to record gait kinematics (Mobility Lab™, APDM Inc). Participants will be reminded to walk at their preferred, comfortable place prior to each walking trial.

The cognitive task will be verbalized serial subtractions from a random three-digit number between 200 and 999, to be provided to the participant prior to each trial. The type of serial subtractions (7's, 3's, 5's or 1's will be determined in a familiarization session completed at the screening visit. Participant responses during each trial will be recorded. We have chosen serial subtractions as the cognitive dual task because: 1) it activates a distributed cortical network including the left dIPFC, 2) is the most widely used dual task paradigm and induces significant and meaningful dual task costs to both postural sway when standing and gait kinematics when walking, in older adults with and without a history of recurrent falls 3) has been used by our team and will thus enable comparison of current results to those from past studies, and 4) is reliable and minimally influenced by learning after familiarization. No instructions will be given regarding task prioritization. This approach has been chosen to most closely mimic real-life situations. Trial order will be randomized for each assessment and at least 1min of rest will be provided in between trials.

Physical Function will be assessed with the Short Physical Performance Battery (SPPB). which is significantly reduced in fallers and predictive of future falls. The SPPB includes measures of standing balance (timing of tandem, semi-tandem, and side-by-side stands, test-re-test correlation=0.97), four-meter walking speed (T-R-T correlation = 0.89), and ability and time to rise from a chair five times (T-R-T correlation = 0.73). SPPB validity has been demonstrated by showing a gradient of risk for admission to a nursing home and mortality along the full range of the scale. In the EPESE population of community-dwelling elders over age 71, the SPPB captured a wide range of functional abilities, and summary scores less than nine independently predicted disabilities in ADL and mobility at one-six years of follow-up.

Mobility will be assessed with the TUG, which requires the participant to stand up from a chair, walk three meters, turn around, walk back and sit down. The average time to complete two separate trials will be recorded. This test has high test-retest reliability and discriminant validity in older adults.

Fear of falling will be assessed by the Falls Efficacy Scale - International (FES-I)

questionnaire, which asks participants how concerned they are of falling during 16 activities. It has excellent internal validity (Cronbach's alpha=0.96) and test-retest reliability (ICC=0.96).

 It correlates with self-reported and assessed functional status, the degree of self-imposed activity restriction in daily life and future falls in older adults.

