#### Inclusion criteria:

#### 4.3

1. Aged 65-85 years.
2. Self-report of two or more falls within the past year. Falls will be defined by any event in which the individual unintentionally comes to rest on the ground or other lower level, not as a result of a major intrinsic event (e.g., syncope) or an overwhelmingly external hazard (i.e., car accident).
3. Self-report of fear of falling, as defined by a "yes" answer to the yes-or-no question "Are you worried that you will fall in the future?"
4. At least some mild performance decrement in physical *and* executive function as defined by A) a score of nine or below on the SPPB (range=0-12, 12 reflecting best

performance), and B) a score below the 75% of performance based upon age- and education-based norms in the Trail Making Test (TMT, part B).

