## 5.1

Cognitive Assessment: Participants will complete a 30-35min battery of cognitive tests that are correlated with dual tasking, functional capacity, and/or falls. We will minimize the potential for procedural learning within this battery by having participants complete the battery as "practice" at the end of the in-person screen. Moreover, tests were selected that have alternate forms, or, were felt to be resistant to practice effects. All tests have excellent psychometric properties and normative data covering the range of demographic characteristics of our proposed sample, with minimal ceiling and floor effects. Tests will include the Trail Making Test (A and B) of executive function (i.e., speeded visual search, vigilance and set-shifting). For this primary outcome, we will utilize the original Test B at baseline, and three alternative forms of Part B, which have comparable psychometric properties, for each of the three follow-ups. Participants will also complete the MoCA test of global cognitive function, WAIS-IV Digit Span (Forwards, Backwards) test of working memory, the WAIS-IV Coding test of sustained attention and motor speed, the Category and Phonemic Fluency tests of semantic knowledge and word retrieval, and the Hopkins Verbal Learning Test – Revised (HVLT-R) of verbal episodic memory. Staff will be trained in all assessment procedures by our co-investigator, [name] (with ongoing supervision to ensure standard administration and scoring).

Mood will be assessed as it influences performance on clinical tests of physical and cognitive function, and long-term exposure to tDCS may affect (i.e., improve) mood. We will use the Center of Epidemiology Studies-Depression Scale Revised (CESD-R) scale, which has been used extensively in epidemiology studies and consists of 20 questions regarding feelings of depression, worthlessness, loneliness, energy level, and fear. The CESD-R has high internal consistency ( $r=0.90$ ) and a test-retest reliability of 0.51.

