#### Overall approach:

Exploratory analyses will be used to assess outcomes distributions, and any necessary transformations (e.g. to combat significant skew) will be performed prior to estimation of mean treatment effects. Said estimation will use **mixed effects linear regression** of post-intervention outcomes immediately following intervention and at three and six months, with random intercepts and slopes to account for serial correlation in repeated measurements on individuals; models will control for baseline outcomes as in analysis of covariance. Owing to the potential for nonlinear trends in outcomes with time, we will assume no functional form of temporal trends. Missing data will be accommodated by multiple (at least 50) imputation of missing records using algorithms to accommodate the clustered nature of the longitudinal design. Analyses will adjust for the stratified design effect (i.e. control for sex). All estimates will be accompanied by 95% confidence intervals (CIs) for the purposes of reporting in publication. Limited hypothesis testing will be performed at the 0.05 level, but emphasis will be on estimation. Owing to the focused nature of the design and prespecification of hypotheses, no interim analyses are planned, and no significance 'adjustment' will be applied for multiplicity.

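### SPPB and TMT are each measured twice before randomisation, but the plan gives the Visit 1 scores no role in the main models, so a modest gain in precision is left unused

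*Combined protocol and SAP*

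**What the plan says.** - **Visit 1 (Study Procedures 5.1, in-person screen).** "The SPPB and the TMT will be completed to ensure at least mild performance decrements" in physical and executive function. The thresholds are in Inclusion criteria 4.3: "a score of nine or below on the SPPB" and, for TMT Part B, "a score below the 75% of performance based upon age- and education-based norms".
- **Familiarization, end of Visit 1.** The cognitive battery is practised to "minimize the effects of procedural learning following the true baseline", which is placed at Visit 3. The TMT is left out of this practice: "They will not repeat the TMT".
- **Visit 3 (baseline assessments).** SPPB and TMT A and B are both measured. For Part B, "we will utilize the original Test B at baseline", with three alternate forms for the three follow-ups.
- **Randomisation (Study design 3.1).** Assignment follows the baseline assessments and the MRI, so both sets of scores precede it.
- **Analysis (Section 6, Overall approach).** "models will control for baseline outcomes as in analysis of covariance". Which visit supplies the baseline value is not spelled out there, and the Visit 1 scores are not mentioned.
- **Power (Aim-specific Analytic Plan).** SPPB: 92% for 0.5 units, with SD 1.5, serial correlation 0.75 and the repeated-measures design. TMT (B minus A): at least 90% for 0.35 SD.

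**The concern.** Every randomised participant will have two pre-randomisation scores on each of these primary outcomes. A covariate measured before randomisation does not bias the comparison of arms, and a second noisy measurement of a stable trait usually predicts follow-up better than one alone. If only the Visit 3 score enters the model, the confidence intervals for the Aim 2 and Aim 3 primary outcomes are somewhat wider than the collected data require. This bears on the plan's own priorities, since the Overall approach puts the emphasis on estimation with 95% intervals. The plan already intends to use one Visit 1 measure in this way: the WTAR reading score is to be an adjustor for change in executive function.

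**Working it through.** **Inputs from the plan.** 57 evaluable per arm, two-sided 0.05, SPPB SD 1.5, SPPB effect 0.5, TMT effect 0.35 SD, serial correlation r = 0.75, three follow-up visits. The plan does not state a correlation for TMT; 0.75 is assumed there too.

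**Formula.** With m follow-ups averaged, k baseline scores as covariates and the same r between every pair, the residual variance as a fraction of SD² is

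F = (1 + (m−1)r)/m − k·r²/(1 + (k−1)r).

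The standard error of the arm difference is SD × √(2F/57), and power is about Φ(effect/SE − 1.96).

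**Step 1: reproduce the stated power (m = 3, k = 1).** F = 2.5/3 − 0.5625 = 0.2708. SE = 1.5 × √(2 × 0.2708/57) = 0.146. Then 0.5/0.146 = 3.42, and power = 92.8%. A 50,000-replicate simulation gives 92.0%. The stated 92% reproduces. TMT gives 94.8%, consistent with at least 90%.

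**Step 2: add Visit 1, equal correlation, no selection (k = 2).** The second term becomes 2 × 0.5625/1.75 = 0.6429.

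| Contrast | F, one baseline | F, two baselines | Cut in variance | SPPB power | TMT power |
|---|---|---|---|---|---|
| One visit | 0.4375 | 0.3571 | 18% | 76.7% to 84.6% | 80.6% to 87.8% |
| Three-visit average | 0.2708 | 0.1905 | 30% | 92.8% to 98.3% | 94.8% to 99.0% |

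At r = 0.75 these are upper limits, because nothing has yet been allowed for the entry criterion or for Visits 1 and 3 being close in time.

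**Step 3: allow for the entry criterion.** Enrolment requires a low Visit 1 score, which truncates that score. The pass rate on SPPB alone is not given. The HIPAA request expects 432 in-person screens, and 144/432 = 33% enrol after all criteria, so the share passing this one criterion should be no lower than about a third. I take 30%, 50% and 75% as the range. For a normal score with pass fraction p, z = Φ⁻¹(p) and λ = φ(z)/p, the retained Visit 1 variance is v = 1 − zλ − λ². Each variance or covariance among the other scores falls by 0.5625 × (1 − v).

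- Once Visit 1 is in the model, selection on it changes nothing: F stays 0.3571 (one visit) and 0.1905 (average).
- With Visit 3 only, F falls. At p = 0.5, v = 0.363, the variance is 0.6417 and the covariance 0.3917, so F = 0.6417 − 0.3917²/0.6417 = 0.4026.
- Cuts at p = 75% / 50% / 30%: 14% / 11% / 9% for one visit and 23% / 19% / 16% for the average.

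**Step 4: let Visits 1 and 3 correlate more closely with each other.** Both precede treatment, while follow-up runs to six months. Keep 0.75 for all other pairs and assume 0.85 or 0.90 between Visits 1 and 3.

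- Without selection, one visit: two-baseline F = 1 − 1.125/1.85 = 0.3919 or 1 − 1.125/1.90 = 0.4079, a cut of 10% or 7%. For the average: 17% or 11%.
- With the entry criterion at 30-75% passing: 4.5-8.6% for one visit and 7.4-14.0% for the average.

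**Step 5: the case of no gain.** Under first-order decay the Visit 1 to follow-up correlation is 0.75 × 0.75 = 0.5625. Given Visit 3, the remaining covariance is 0.5625 − 0.75 × 0.75 = 0, so Visit 1 adds nothing. In between, without selection, a Visit 1 to follow-up correlation of 0.65 gives a 6% cut for the average, and 0.70 gives 16%.

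**In interval width.** Width scales with the square root of the variance ratio. The Step 3 cuts narrow intervals by about 5-7% (one visit) and 8-12% (average). The Step 4 cuts with selection narrow them by about 2-4% and 4-7%.

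**The case against.** The strongest reply is that nothing here is wrong. Analysis of covariance on one designated baseline is standard, the power target is met without Visit 1, and preferring Visit 3 is sensible because Visit 1 is both the selection visit and the first exposure to the TMT. All of that stands. It limits the point to an efficiency gain; it does not make the second covariate harmful, since selection and practice before randomisation are common to both arms.

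The TMT part is open to further objections, and they stand:
- Eligibility uses Part B, while the outcome is B minus A. Part A at Visit 1 is implied by the reference to the TMT but not spelled out.
- Four Part B forms are named for five administrations, so the form used at Visit 1 is not stated.
- A first-exposure score may correlate less with follow-up, and the planned WTAR adjustment may already carry some of the same information.

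A reader might also infer four stronger things that the documents do not support:
- *That selecting on Visit 1 makes the Visit 3 baseline noisier and so the loss larger.* Step 3 shows the reverse: truncation lowers what Visit 1 can add.
- *That the trial is underpowered for its SPPB and TMT claims.* The stated power is for the repeated-measures design and reproduces. No single-visit power is claimed for these outcomes.
- *That the duration-of-effects objective is at risk.* That wording is in the Aim 1 paragraph, on dual-task costs, which this change does not touch. Aim 2 reuses the same mixed model, so visit-specific SPPB contrasts may be reported, but the plan does not rest a power claim on them.
- *That the Visit 1 scores are certainly discarded.* The text is silent rather than explicit. Further covariates for sensitivity analyses are said to be in a Section 3.3.7.3 that is not in the supplied text.

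**Conclusion.** The point holds as a modest loss of precision that saves nothing. It is not a bias, an error in the analysis or a fault in the sample size. Cuts of 18% and 30% are the ceiling at the protocol's correlation of 0.75 and need equal correlation and no effect of the entry criterion. About 9-14% (one visit) and 16-23% (average) is reasonable once the criterion is allowed for, about 5-9% and 7-14% if the two pre-treatment scores are also closer to each other than to follow-up, and the gain could be nil. The pass fraction, the 0.85-0.90 correlation and the use of 0.75 for TMT are assumptions. The conclusion is firmest for SPPB and less certain for TMT.

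**What to change.** In Section 6, Overall approach, add before unblinding that the SPPB model adjusts for the Visit 1 and Visit 3 scores as two separate covariates. Say that the TMT (B minus A) model does the same, provided Part A is recorded at Visit 1, and state which Part B form is used there. Separate terms let the data weight the truncated SPPB score and the first-exposure TMT score; a simple average would force equal weights. Define Visit 3 as the baseline for reporting and for describing change.

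The cost is one sentence and one degree of freedom per model, against about 114 evaluable participants. No visit, test or participant is added. The sample size and the stated power need no change. Timing matters: if the covariate is added after unblinding, it will look data-driven.
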